Appendix 2. Schedule of Events (Donor)

Transplant Study Day		-1	0	12										Unscheduled Visit within 3 months of transplant	Unscheduled Visit greater than 3 months from transplant		
Transplant Study Week					4-6	8	12										
Transplant Study Month						2	3	6	9	12	18	24					
Visit Number		00	01	02	03	04	05	06	07	08	09	10					
GENERAL ASSESSMENTS																	
Demographics	Age, Race, Ethnicity, Gender		X														
Donor Information	Cause of Death		X														
LOCAL LABORATORY ASSESSMENTS																	
Blood Type	A, B, O, Rh		X														
HLA Typing	I (A, B, C), II (DR, DP, DQ)		X														
Viral Panel	CMV IgG, EBV IgG, HBsAg, HBcAb, HCV Ab, HIV		X														
MECHANISTIC ASSAYS – ISMMS (PI: [name])																	
T Cell Function (ELISPOT)	Blood or Spleen		X														
Blood to Archive	Biospecimen Repository-ISMMS		X

1. PROTOCOL SYNOPSIS

Title	B cell Targeted Induction to Improve Outcomes in Pediatric Lung Transplantation
Clinical Phase	Phase 2
Number of Sites	7 US Sites
IND Sponsor/Number	NIAID/IND Number 121403
Primary Study Objective	To determine whether rituximab induction along with standard of care immunosuppression will improve outcomes following pediatric lung transplantation.
Secondary Study Objectives	
 1. To determine the effects of rituximab induction on post-transplant immunity in pediatric lung transplant recipients. 2. To assess the safety and tolerability of rituximab. 3. To assess the feasibility of a phone based intervention to decrease tacrolimus trough level variability.
Study Design/Treatment Description	Phase 2, prospective, multi-center, double-blind, randomized, placebo-controlled clinical trial in which 50 primary pediatric lung transplant recipients will be randomized (1:1) to receive either induction therapy with anti-CD20 mAb (375 mg/m ²) IV or placebo (IV day 0 and day 12 post-transplant) plus standard of care immunosuppression (thymoglobulin induction, tacrolimus or generic equivalent, MMF or generic equivalent, and steroids).
Primary Endpoint	
The primary endpoint is a composite of the earliest time to any of the following events during the follow-up period:
 
 • Chronic Allograft Dysfunction • Listed for Retransplant • Death
Secondary Clinical Endpoints	
 1. Post-transplant clinical outcomes including: 
 a. Incidence of chronic allograft dysfunction, listing for retransplantation, and death during the follow-up period, which will be a minimum of 12 months post-transplant b. Incidence of Primary Graft Dysfunction c. Incidence of Grade A Acute Rejection during the follow-up period, which will be a minimum of 12 months post-transplant d. Incidence of Antibody Mediated Rejection during the follow-up period, which will be a minimum of 12 months post-transplant e. Incidence of tacrolimus variability threshold during the follow-up period, which will be a minimum of 12 months f. Percentage of participants meeting tacrolimus variability threshold who complete tacrolimus variability intervention

	
 g. Magnitude of change in standard deviation of tacrolimus levels following intervention 
2. Post-transplant safety outcomes including:
 
 a. Incidence and severity of infection episodes b. Serious adverse events related to rituximab
Secondary Mechanistic Endpoints	
 1. Incidence and kinetics of DSA and autoantibodies, specifically Collagen V (ColV) and k-alpha-1 tubulin (kα1T) 2. Frequency, kinetics, phenotype and function of peripheral B cells 3. Frequency, kinetics and cytokine profiles of allo- and auto reactive T cells 4. Incidence and quantity of B cells and B cell proximity to other cells in the graft tissue
Accrual Objective	50 randomized pediatric lung transplant recipients
Study Duration	
4.5 years (3.5 year accrual + 1-4.5 year follow-up period)
 
All participants will be followed for a minimum of 1 year post-transplant. Participants will continue follow-up visits (up to 4.5 years post-transplant) until the last participant completes 1 year of follow-up.

Enrollment Inclusion Criteria	
 1. Subject and/or parent/guardian must be able to understand and provide informed consent 2. Less than or equal to 21 years of age 3. Candidate for primary lung transplant (listed for lung transplant) 4. Female and male subjects with reproductive potential must agree to use FDA approved methods of birth control for 12 months after completion of treatment 5. Adequate bone marrow function based on the following criteria: 
 a. ANC > 1000mm³ b. Platelets > 100,000/mm³ c. Hemoglobin > 7 g/dL d. AST or ALT <2x Upper Limit of Normal unless related to primary disease
Enrollment Exclusion Criteria	
 1. Inability or unwillingness of a participant to give written informed consent or comply with study protocol 2. Multi-organ transplant 3. Previous treatment with rituximab (Rituxan®) 4. History of severe allergic anaphylactic reactions to humanized or murine monoclonal antibodies 5. History of severe reaction to previous therapy with IVIG 6. History of Burkholderia cenocepacia 7. History of anti-CD20 therapy

	
 8. Persistent hypogammaglobulinemia (IgG < lower level of normal for age based on local laboratory ranges or 400 g/dL for >2 months) and/or IVIG replacement therapy 9. Positive blood culture, sepsis or other disease process with hemodynamic instability at time of enrollment 10. Any history of serologic positivity to HIV, HBsAg, HBcAb and HCV Ab 11. History of malignancy less than 2 years in remission of malignancy (any history of adequately treated in-situ cervical carcinoma, or adequately treated basal or squamous cell carcinoma of the skin will be permitted) 12. Any condition, including psychiatric disorders, that in the opinion of the investigator would interfere with the subject's ability to comply with study requirements 13. Participation in another investigational trial within 4 weeks of enrollment 14. Currently lactating or plans to become pregnant during the timeframe of the study follow-up period 15. Past or current medical problems or findings from physical examination or laboratory testing that are not listed above, which, in the opinion of the investigator, may pose additional risks from participation in the study, may interfere with the participant's ability to comply with study requirements or that may impact the quality or interpretation of the data obtained from the study

Randomization Inclusion Criteria
	
 1. Serum IgG immunoglobulin level greater than lower level of normal for age based on local laboratory ranges or 400 mg/dL within 90 days prior to randomization 2. Female subjects of childbearing potential must have a negative pregnancy test within 48 hours of transplant 3. Negative for Hepatitis B infection (if at time of transplant, subject does not exhibit effective immunization, the subject should be re-tested)

Randomization Exclusion Criteria
	
 1. Use of an induction agent other than Thymoglobulin® 2. Renal insufficiency requiring hemodialysis or ultrafiltration 3. Inability to obtain intravenous access 4. Positive blood culture, sepsis or other disease process with hemodynamic instability at time of transplant 5. Use of investigational agent(s) within 5 half-lives of the investigational drug or 4 weeks, whichever is longer 6. Receipt of a MMR vaccine within 30 days prior to randomization 7. Any condition that, in the opinion of the investigator, would interfere with the subject's ability to comply with study requirements

Study Stopping Rules
	
Satisfaction of any of the following stopping rules in study subjects at any time of follow-up in the treatment arms will trigger an ad hoc DSMB Safety Review:

	
• Any occurrence of confirmed PML• Incidence of death of 30% or more subjects• Incidence of at least mild acute rejection of 35% or more• Incidence of humoral rejection of 25% or more• Incidence of primary graft dysfunction of 50% or more• Incidence of PTLD of 5% or more• Incidence of infections of any type requiring hospitalization of 40% or more
Individual Subject Stopping Rules	
Individuals who meet any of the criteria listed below will not receive the second dose of rituximab
 
1. Serious adverse event casually related to the rituximab infusion2. Acute pulmonary infectious process with evidence of graft dysfunction3. Positive blood culture, sepsis or other disease process with hemodynamic instability4. Renal insufficiency requiring hemodialysis or ultrafiltration5. Inability to obtain intravenous access6. Use of an investigational drug after the first dose of placebo or rituximab7. Any other event which in the opinion of the principal investigator may pose additional risk to the participant

2. INTRODUCTION

This statistical analysis plan includes pre-planned analyses related to the study objectives outlined in the protocol.

3. GENERAL ANALYSIS AND REPORTING CONVENTIONS

The following analyses and reporting conventions will be used:

- Categorical variables will be summarized using counts (n) and percentages (%) and will be presented in the form “n (%).” Percentages will be rounded to one decimal place.
- Numeric variables will be summarized using n, mean, standard deviation (SD), median, minimum (min), maximum (max). The min/max will be reported at the same level of significance as original data. The mean and median will be reported at one more significant digit than the precision of the data, and SD will be reported at two more significant digits than the precision of the data.
- The median will be reported as the average of the two middle numbers if the dataset contains an even number of observations.
- Test statistics including *t* and *z* test statistics will be reported to two decimal places.
- *P*-values will be reported to three decimal places if greater than or equal to 0.001. If less than 0.001, the value will be reported as “<0.001.” A *p*-value can be reported as “1.000” only if it is exactly 1.000 without rounding. A *p*-value can be reported as “0.000” only if it is exactly 0.000 without rounding.

If departures from these general conventions are present in the specific evaluations section of this SAP, then those conventions will take precedence over these general conventions.

4. ANALYSIS SAMPLES

Intent-to-Treat (ITT) Sample – The ITT sample is all randomized subjects who receive at least a portion of the initial rituximab/placebo infusion. This sample will be used for evaluation of the primary and secondary clinical endpoints. Subjects will be analyzed in the group to which they were randomized, regardless of compliance with the protocol or withdrawal from the study.

Per-Protocol (PP) Sample – The PP sample is the subset of subjects from the ITT sample who complete the full induction protocol, with complete administration of the prescribed dose at both the initial and subsequent infusions, and do not have any major protocol deviations that impact the subject’s evaluability for the primary endpoint. This sample will capture subjects who both tolerate rituximab well and recover as expected from their transplant.

Screening Sample – All consented (i.e., enrolled) subjects will constitute the screening sample. This sample will be used to describe population characteristics.

Safety Sample – All subjects from the screening sample who have the pre-transplant blood draw performed will constitute the safety sample. This sample will be used for all safety summaries. Subjects in this sample who were randomized will be analyzed in the group to which they received, regardless of which group they were randomized to, compliance with the protocol, or withdrawal from the study. If a subject received any rituximab the subject will be analyzed with the rituximab group.

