7.3. Prohibited Medications

The following is a list of prohibited medications:

- Induction agent, other than Thymoglobulin®;
- Other investigational agents;
- Rituximab (Rituxan®), except for treatment of PTLD or treatment of AMR as described in section 7.4.2;

- IVIG, except for treatment of post-transplant hypogammaglobulinemia or humoral rejection as described in sections 7.4 and 7.5.2.

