III: Humoral rejection	
 1. Pulse steroids (10 mg/kg) day 1-3. 2. Plasmapheresis x 5 days without IgG replacement. 3. Bortezomib (1.3 mg/M²) on days 1, 4, 8, & 11 (given after plasmapheresis) with IgG replacement after last dose of Bortezomib. 4. Rituximab (375 mg/m²) weekly weeks 1-4 for patients >1 month post-transplant.

Table 6: Treatment for Antibody Mediated Rejection

Subjects will be monitored for clinical improvement following treatment of AMR. Sites will consider repeat PRA for DSA at 1, 4 and 8 weeks post intervention and/or repeat biopsy for persistent symptoms.

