6.2. Treatment Adherence

Treatment Groups:

- **Rituximab Group** – induction therapy with anti-CD20 mAb (375 mg/m²) IV on day 0 and day 12 post-transplant plus standard of care immunosuppression (thymoglobulin induction, tacrolimus or equivalent, MMF or equivalent, and steroids).
- **Placebo Group** – induction therapy with placebo IV on day 0 and day 12 post-transplant plus standard of care immunosuppression (thymoglobulin induction, tacrolimus or equivalent, MMF or equivalent, and steroids).

Randomization to one of the two groups will occur once the subject has received the transplant and is deemed hemodynamically stable. The first infusion must be administered within 12 hours of returning to the ICU following transplant. The second infusion should be administered on day 12 (\pm 2 days) post-transplant.

Adherence will be summarized for the ITT sample. The status of each infusion will be classified as complete, partial, or not done and the duration (or extent) of exposure will be calculated by determining the number of days between first and second infusions (+1) for each subject in the

sample. These variables will then be summarized using appropriate statistics in a table and subject-level details will be presented in a listing.

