7.3.2. Post-transplant Safety Endpoints

The safety sample will be used for analysis of these post-transplant safety endpoints.

Variable: Incidence and severity of infection episodes

Analysis: We will analyze each type of infection separately (bacterial, fungal, or viral, including RVI, CMV, and EBV), as well as for all types of infections combined. We will first determine the incidence of bacterial, fungal and viral infections in the rituximab and control groups using a combination of information from both the local, clinical site and the viral detection core laboratory. The presence of an infection at a given time point will be defined as follows:

- A local report of infection through either the organism specific CRF page or adverse event reporting;
- Presence of symptoms at the time of a study visit without a local report of infection but with a corresponding core lab identified infection.
 - All symptoms reported at the time of a study visit will be considered for any EBV and CMV infections identified by the core lab.
 - For any other infections identified in core lab NP and BAL samples, shortness of breath, new x-ray or other imaging finding, new supplemental oxygen requirement, cough with sputum, and decreased spirometry will be the only symptoms considered.

‘Incidence rate’ will be the number of infections per patient-month, and we will focus on the estimates and associated 90% confidence intervals for the ratio of such rates (RR), where $RR > 1.0$ indicates greater infection rates for rituximab. Of course, infection events are biologically related within patient, thus, relative to perfect independence of events, greater proportions of patients will experience more episodes of the same type of infection and greater proportions of patients will experience no episodes. Accordingly, Poisson regression models offset for months of follow-up and adjusted for overdispersion will be used to compare groups on the rate of each type of infection and any infection.

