8.2. Adverse Events

Per the protocol, only AEs with a severity grade of 3 or higher will be collected. All AEs will be classified by system organ class (SOC) and preferred term (PT), according to the Medical Dictionary for Regulatory Activities (MedDRA) version 17.0. The severity of AEs will be classified using the National Cancer Institute's (NCI's) Common Toxicity Criteria for Adverse Events (CTCAE) version 4. Each AE will be recorded once at the highest severity.

AEs will be collected from the time of enrollment through study termination. Treatment-emergent AEs will be identified as those with an onset date on or after the initial infusion as well as those with onset before the initial infusion but that continued and worsened in severity after the initial infusion. If the start of the AE in relation to the start of study medication cannot be established (e.g., the start date for the AE is missing), then the AE will be considered as having an unknown timing relative to treatment and will be presented in a separate column in the same table as treatment-emergent AEs. All data tabulations will be of only treatment-emergent events and stratified by treatment group while non-treatment-emergent AEs will be listed separately.

An overall summary table will be developed to report the number of events and the number and percentage of subjects having at least one event in the following categories:

- AEs
- AEs indicated as serious
- AEs that lead to study drug discontinuation
- AEs with an outcome of death
- AEs that were reported as being related to rituximab/placebo, blood draw, or bronchoscopy
- AEs reported by severity and maximum severity

In general, when reporting on the relationship of an adverse event to study drug and procedures, the DAIT MM assessment of relationship will be used for all serious AEs and the site investigator assessment of relationship will be used for all non-serious AEs. This convention will apply even when AEs are summarized in aggregate (i.e., serious and non-serious AEs pooled together).

Additionally, the classification of AEs by MedDRA SOC and PT will be summarized for each treatment group and overall. Summary tables will present the total number of events as well as the number and percentage of subjects experiencing at least one event in each SOC/PT combination.

Separate data listings may be generated for treatment-related AEs and AEs leading to study drug discontinuation.

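### The SAP's safety grouping rule counts any rituximab, so a placebo participant given open-label rituximab for AMR or PTLD would move to the rituximab group with their whole record

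*SAP*

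**What the plan says.** SAP Section 4 groups the safety sample by treatment received: "Subjects in this sample who were randomized will be analyzed in the group to which they received". It then adds: "If a subject received any rituximab the subject will be analyzed with the rituximab group". Neither sentence says which rituximab counts, by source, indication or timing.

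The protocol foresees rituximab outside the blinded infusions. Section 7.3 prohibits it "except for treatment of PTLD or treatment of AMR as described in section 7.4.2". (There is no Section 7.4.2; treatment of AMR is in 7.5.2.) Table 6 in Section 7.5.2 lists rituximab for stage III humoral rejection, "weekly weeks 1-4 for patients >1 month post-transplant", with no restriction by arm.

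SAP 6.2 defines the two groups by the induction infusions; the placebo group is "induction therapy with placebo IV on day 0 and day 12 post-transplant" plus standard immunosuppression. Section 4 does not refer to that definition.

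The safety sample feeds the infection and related-SAE comparisons (SAP 7.3.2) and the adverse event tables (SAP 8.1 and 8.2). The infection incidence rate "will be the number of infections per patient-month", compared by a rate ratio with a 90% confidence interval. For adverse events, "Treatment-emergent AEs will be identified as those with an onset date on or after the initial infusion", and "All data tabulations will be of only treatment-emergent events and stratified by treatment group".

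The documents also define the safety sample differently. Protocol 13.4.1 makes it identical to the ITT sample, meaning randomised participants who received at least part of the first infusion. SAP Section 4 uses every consented participant who had the pre-transplant blood draw.

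**The concern.** An as-treated rule for safety is ordinary when it deals with dosing errors. This one, read literally, also captures treatment given later because the graft did badly or PTLD developed. Only placebo participants can change group, and they change because of a post-randomisation outcome, so the shift runs one way.

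They also move with their entire record. Treatment-emergence starts at the first study infusion, so events on placebo before any rituximab would be counted against rituximab. For AMR, the timing in Table 6 means that at least a month of placebo time moves.

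The affected analyses address secondary objective 2, safety and tolerability. If participants with AMR or PTLD have more infections than others, rituximab induction will look less safe than it is. The effect on rituximab-related SAEs is limited, because the medical monitor decides attribution.

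A smaller point follows from the two sample definitions. Someone randomised but never infused is in the SAP's safety sample if the blood draw was done, but received neither treatment and so has no stated group.

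**Working it through.** The plan gives no figure to reproduce here: no document states how often open-label rituximab is expected or how handling it affects the analysis. The text is checked first; the arithmetic then shows only how large the effect could be.

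**Text.** Within SAP Section 4, the ITT sample is tied to the initial rituximab/placebo infusion and the per-protocol sample to both infusions. The safety rule has no such tie. No passage of the SAP says how open-label rituximab is handled in the safety analyses. The protocol's own safety sample has no reassignment rule.

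**Inputs.** 25 participants per arm (Protocol 13.6); infections per patient-month as the estimand (SAP 7.3.2). Assumed: equal follow-up, no true effect of induction on infection, rate 1 in most participants, and rate *k* in the *m* participants who receive open-label rituximab.

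**Case A: *m* recipients in each arm.** Grouped by study infusion, the rate ratio is 1.00. Under the literal rule the rituximab group has 25 + m people, of whom 25 − m have rate 1 and 2m have rate k. The placebo group keeps 25 − m people at rate 1. So

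RR = [(25 − m) + 2mk] / (25 + m)

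| m | k = 1 | k = 2 | k = 3 |
|---|---|---|---|
| 1 | 26/26 = 1.00 | 28/26 = 1.08 | 30/26 = 1.15 |
| 2 | 27/27 = 1.00 | 31/27 = 1.15 | 35/27 = 1.30 |
| 4 | 29/29 = 1.00 | 37/29 = 1.28 | 45/29 = 1.55 |

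**Case B: all *m* recipients in the placebo arm**, the extreme of what the trial's hypothesis would produce. As randomised, RR = 25/(25 − m + mk); under the rule, RR = (25 + mk)/(25 + m). With m = 2 and k = 2 these are 25/27 = 0.93 and 29/27 = 1.07, so the direction reverses.

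**Effect on the interval in Case A.** Simulation used 6,000 trials per setting, follow-up uniform on 12 to 54 months, base rate 0.1 or 0.3 infections per month, between-participant (gamma) variance 0.5 or 1.0, and an overdispersion-adjusted Poisson 90% interval. The base rates and variances are assumptions. Shares of trials with the interval wholly above 1, although there is no effect:

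| Grouping | Share |
|---|---|
| By study infusion | about 4–7% (nominal 5%) |
| Literal rule, m = 1, k = 2 | 9–11% |
| Literal rule, m = 2, k = 2 | 12–15% |
| Literal rule, m = 4, k = 2 | 16–24% |
| Literal rule, m = 4, k = 3 | 28–45% |

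A second simulation (4,000 trials per setting, base rate 0.15, variance 0.5) let each participant receive open-label rituximab with probability 5%, 10% or 25%. With k = 2 the shares were 11%, 17% and 32%, against 6–7% when grouped by study infusion. With k = 1 the two groupings did not differ materially (about 6% each). At those probabilities the chance that at least one of 25 placebo participants moves is 1 − 0.95²⁵ = 72%, 1 − 0.90²⁵ = 93%, and over 99%. The 5% and 25% ends are the stopping thresholds for PTLD and humoral rejection, borrowed only to span a range; they are not expected rates of rituximab use.

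**The case against.** The strongest reply is that the authors meant study drug. Elsewhere the documents use rituximab as shorthand for the study infusion, for example in the individual stopping rules and in the participant replacement rule. The disputed sentence follows an as-treated rule, and SAP 6.2 defines the groups by induction. On that reading it settles only partial or mis-dispensed study doses. This is plausible, but it is not written, and a programmer working from concomitant medication data could apply the literal rule.

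Second, few participants may be exposed. Stage III humoral rejection needs antibody, abnormal histology and graft dysfunction together, and no rate is given. This stands: the rows with m = 4 have no documentary support.

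Third, the illustration applies the raised rate from day 0. If a doubling held for only half of follow-up, the average multiplier would be 1.5 and the ratios would be 27/26 = 1.04 (m = 1) and 29/27 = 1.07 (m = 2). About 7–8% and 9–10% of simulated intervals would then lie wholly above 1, against 5–7% when grouped by study infusion. That is a fair lower version of the same effect.

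Fourth, infections after an open-label dose do occur in someone exposed to rituximab, and grouping by study infusion counts that time as placebo. That is a reason to report those events separately. It does not justify moving the placebo time before the dose.

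On the never-infused participant, the adverse event tables hold only treatment-emergent events, so none of theirs would enter. The denominator and the group label remain undefined.

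**Conclusion.** The concern holds. As written, the rule reassigns placebo participants on the basis of a bad outcome, in one direction only, and takes their pre-exposure record with them. The infection rate ratio, the infection severity comparison and the treatment-emergent adverse event tables could each be biased against rituximab. The primary and secondary clinical endpoints, including AMR and death, are analysed as randomised in the ITT sample, and the stopping rules run by randomised arm, so they are untouched. Beyond the adverse event tables, PTLD has only a listing.

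The size cannot be known from the documents. If nobody moves there is no bias, and if open-label recipients have no higher infection rate than the others the expected rate ratio stays 1.00. With one or two recipients per arm at twice the rate throughout, a null ratio shifts to 1.08 or 1.15. These figures illustrate the possible effect; they do not show that bias is likely. The point should be fixed because the rule can give a wrong answer as it stands and the repair is small. Confidence is medium, since the authors may have intended study infusions only.

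**What to change.** In SAP Section 4, limit the sentence to participants who received any rituximab as a blinded study infusion (day 0 or day 12). State that open-label rituximab does not change the safety group. Flag those participants and show their events before and after the open-label dose in a supporting table.

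Reconcile SAP Section 4 with Protocol 13.4.1. Use participants who received at least part of a study infusion as the denominator for by-group tables, and list other consented participants' events separately, as SAP 8.2 already does for adverse events that are not treatment-emergent. Correct the cross-reference in Protocol 7.3 at the same time.

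The cost is a few words, one population flag and one supporting table. The change should be made before unblinding, so that the grouping is not chosen with the results in view. It concerns the analysis only and leaves trial conduct and participants' care as they are.
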